## 7.0 Reporting of Adverse Events or Unanticipated Problems involving Risk to Participants or Others

### Definition of Adverse Event (AE)

An AE is any untoward medical occurrence (e.g., noxious or pathological changes) in a subject compared with pre-existing conditions that may occur during any part of the clinical study. An AE is defined as being independent of assumption of any causality (e.g., primary or concomitant disease or study design). AEs are evaluated by the Investigator and maintained in the research records at the site.

### Definition of Serious Adverse Event (SAE)

An SAE is an AE occurring during any study phase (i.e., run-in, treatment, follow-up), that fulfills one or more of the following criteria:

- Results in death
- Is immediately life-threatening
- Requires in-patient hospitalization or prolongation of existing hospitalization
- Results in persistent or significant disability or incapacity
- Is a congenital abnormality or birth defect
- Is an important medical event that may jeopardize the patient or may require medical intervention to prevent one of the outcomes listed above.

### Procedures for Reporting Adverse Events (AEs)

All SAEs are be reported to the Vanderbilt University Medical Center (VUMC) Clinical Research Enterprise, whether or not considered causally is related. The

site investigator is responsible for informing their local IRB as per local requirements.

Investigators and other center personnel must inform appropriate Clinical Research Enterprise representatives via REDCap of any SAE that occurs in the course of the study within 1 day (i.e., immediately but no later than the end of the next business day) of when he or she becomes aware of it. Follow-up information on SAEs must also be reported by the Investigator within the same time frame.

An automated email alert will be sent to the designated Clinical Research Enterprise representative, when the page with SAE information is saved in REDCap by the Investigators or other site personnel. If REDCap is not available, then the Investigator or other study site personnel reports by fax an SAE to the appropriate Clinical Research Enterprise representative. A paper back- up SAE report is used for this purpose. The same reporting time frames still apply. The investigator is responsible for completing the eCRF as soon as the system becomes available again.

The Clinical Research Enterprise representative will work with the Investigator to compile all the necessary information and ensure that all the necessary information is provided to Vanderbilt University Medical Center within one calendar day of initial receipt for fatal and life-threatening events and within five calendar days of initial receipt for all other SAEs.

### **Reporting of serious adverse events to the FDA**

The Sponsor will inform the regulatory authorities of any serious or unexpected adverse events that occur in accordance with the reporting obligations of 21 CFR 312.32. It is the responsibility of the investigator to compile all necessary information and ensure that the FDA receives a report according to the FDA reporting requirement timelines.

### **Protocol Deviations**

Investigators are required to adhere to the protocol, applicable federal (national) or state/local laws and regulations, and any conditions required by the IRB/Medical Ethics Committee (MEC), or applicable regulatory authorities.

A protocol deviation is used to describe situations in which the clinical protocol was not followed. All deviations from the protocol must be reported to Vanderbilt study staff per 21 CFR §812.150. In addition, all deviations must be reported to the reviewing IRB per the IRB's reporting requirements. The investigator shall state any mitigating circumstances or clinical reasoning that resulted in a protocol deviation. Examples of deviations would be required testing not done or an intervening medical condition preventing return for follow-up during the specified window.

The investigator must notify Vanderbilt study staff and the reviewing IRB of any deviation from the investigational plan to protect the life or physical well-being of a patient in an emergency as soon as possible, but not later than 5 working days after the deviation has occurred, or no later than 5 working days after the investigator becomes aware of the deviation.

## **8.0 Monitoring of the study**

During the study, a Clinical Research Enterprise representative will conduct regular monitoring visits with the study site. The monitoring visits may be conducted by phone, e-mail or by in-person visits to the study site. The monitoring visits will:

- Provide information and support to the investigator(s)
- Confirm that facilities remain acceptable
- Confirm that the investigational team is adhering to the protocol, that data are being accurately and timely recorded in the eCRF.
- Perform source data verification (a comparison of the data in the eCRF with the patient's medical records at the hospital or practice, and other records relevant to the study) including verification of informed consent of participating patients.

The Clinical Research Enterprise representative will be available between visits if the investigator(s) or other study site personnel need information and advice about the study conduct.

## **9.0 Data Management**

Data management will be performed by the Clinical Research Enterprise staff. Data will be entered into REDCap, a web-based data capture system at the study site. Trained site staff will be responsible for entering data on the observations, tests and assessments specified in the protocol into REDCap. Data entered in the REDCap will be saved to a central database and changes tracked to provide an audit trail. The data will then be source data verified, reviewed/queried and updated as needed. The Principal Investigator is responsible for electronically signing the eCRF. Data queries will be issued for inconsistent, improbable or missing data. All entries to the study database will be available in an audit trail. The data will be frozen and then locked to prevent further editing. When all data have been coded, validated, signed, and locked, a clean file will be declared. Any treatment revealing data may thereafter be added and the final database will be locked. A copy of the eCRF will be archived at the study site when the study has been locked.

### **Source data**

The Clinical Trial Agreement (CTA) will specify the location of source data. Access to source documents and source data is essential to inspection and review of clinical studies by the Food and Drug Administration (FDA).

### **Recording of data**

The REDCap Web-Based Data Capture system will be used for data collection and query handling. The site Principal Investigator will ensure that data are recorded in the electronic Case Report Forms (eCRF) and will ensure the accuracy, completeness, and timeliness of the data recorded and of the provision of answers to data queries according to the Clinical Trial Agreement.

Data will be entered in the eCRF by trained personnel using the REDCap system. When data have been entered, reviewed, edited, and source data verification has been performed, as appropriate, by a VUMC Clinical Research Enterprise representative, the data will be frozen to prevent further editing. The site Principal Investigator will be notified to sign the eCRF electronically. A copy of the eCRF data will be archived at the study site.

### **10.0 Study Withdrawal/Discontinuation**

Participants may withdraw consent at any time for any reason or be dropped from the trial at the discretion of the investigator should any untoward effect occur. In addition, a subject may be withdrawn by the investigator or the Sponsor if enrollment into the trial is inappropriate, the trial plan is violated, or for administrative and/or other safety reasons.

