#### 2. Secondary

- a. All-cause mortality
- b. Survival to transplantation
- c. LVAD related complications
  - i. Stroke
  - ii. Transient ischemic attack
  - iii. Mucocutaneous bleeding
  - iv. Right ventricular failure
  - v. Infection: LVAD system related
  - vi. Moderate or Severe aortic insufficiency
- d. Changes in biomarkers

- e. Re-hospitalizations
- f. Echocardiographic changes in myocardial structure and function
- g. Functional status
  - i. NYHA functional class
  - ii. 6-minute walk test
- h. Quality of life
  - i. KCCQ

**Design:** This is a pilot 2-arm prospective randomized controlled trial. Both treatment strategies, Lavare cycle on and off, are consistent with standard of care.

**Study Population:** This trial will enroll patients undergoing their first HeartWare LVAD implantation as well as those chronically supported with HeartWare LVAD. Clinical data will be collected at baseline and at regular post-enrollment follow-up until trial ends. For chronically supported patients, minimum support duration of 3-months will be required.

**Duration of follow-up:** 180-days; follow-up visits will be logged at 30-days, 90-days and 180-days.

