#### Procedures for randomization

Using REDCap, participants will be randomly assigned in a 1:1 ratio. Participants will receive a randomization number. The randomization number identifies the participant for all procedures occurring after randomization. Once a randomization number is assigned to a participant, it cannot be re-assigned to another participant.

There are 2 arms:

- 1) LavareTM Cycle - On  
**OR**
- 2) LavareTM Cycle – Off

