## 5.0 Study Procedures

Screening Visit: Visit 1 (prior to new LVAD implantation for New Implants and at the time of consent for Previous Implants)

- Informed Consent
- Demographics
- Review of Medical History
- Blood sampling for biomarkers (approximately 20mLs)
- KCCQ questionnaire
- 6-minute walk test (Can be deferred if patient is on inotropic or MCS support)
- NYHA functional class assessment defined as follows:
  1. Class I - No symptoms and no limitation in ordinary physical activity, e.g. shortness of breath when walking, climbing stairs etc.
  2. Class II - Mild symptoms (mild shortness of breath and/or angina) and slight limitation during ordinary activity.
  3. Class III - Marked limitation in activity due to symptoms, even during less-than-ordinary activity, e.g. walking short distances (20-100 m). Comfortable only at rest.
  4. Class IV - Severe limitations. Experiences symptoms even while at rest. Mostly bedbound patients.
  5. No NYHA class listed or unable to determine.

Data will be collected on the following tests that were likely performed as part of the standard LVAD evaluation. The participant will not be required to undergo these tests for the purposes of this trial:

- Echocardiogram
- Right heart catheterization or Swan-Ganz Catheterization

The Screening Visit and the Randomization Visit can occur on the same day, if all study criteria have been met.

The following will happen:

- Randomization: Randomly assigned by REDCap to one of the two groups:  
1Lavare™ Cycle - On  
**OR**  
2 Lavare™ Cycle – Off
- Study intervention: Changes in Lavare™ Cycle will be made by the study staff according to the group you are assigned.
- LVAD data: standard parameters displayed on the screen upon routine interrogation of the LVAD will be collected.

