## 6.0 Risks

We do not have data to detail potential risks and their chances arising from participation in this study. This study aims at understanding this very question.

Hypothetically, conditions that lead to decreased blood volume in the left side of the heart (such as dehydration, excessive bleeding, right HF, fluid around the heart, etcetera) can increase the chances of suction events or low flow alarms with implementation of the Lavare™ Cycle.

1. Suction event occurs when decreased blood volume in the left side of heart causes part of left heart wall *sucked over* the LVAD pump's inflow cannula; the result of this event is reduction in LVAD pump speed to reduce the suction pressure and free up the sucked over left heart wall.
2. Low flow alarm is triggered when average flow through the pump drops below the set limit.

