### **11.0 Statistical analysis**

Statistical analysis will be performed using software STATA version 13 (StataCorp, College Station, TX). Baseline characteristics will be compared using Wilcoxon-Rank Sum test for continuous variables and Fisher's exact test for categorical variables. Multivariable regression analyses will be performed to assess for risk of primary and secondary outcomes with Lavare cycle on and off. Changes in laboratory parameters, echocardiographic measures, functional status and quality of life will be assessed using multivariable regression analyses. Statistical significance will be defined as  $p<0.05$ .

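### Section 10.0 lets participants be dropped from the trial after an untoward effect or a plan violation, and nothing requires later outcomes to be collected or all randomised participants to be analysed as assigned

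*Combined protocol and SAP*

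**What the plan says.** Section 10.0 gives two routes out besides the participant's own withdrawal of consent, which is not at issue here. Under the first, a participant may be "dropped from the trial at the discretion of the investigator should any untoward effect occur". The second route is open to two parties and has wider grounds: "a subject may be withdrawn by the investigator or the Sponsor if enrollment into the trial is inappropriate, the trial plan is violated", and the clause goes on to list administrative and other safety reasons. In both routes the person leaves the trial; the clause does not speak of leaving the assigned setting only.

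Other sections that bear on this:

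- **Section 2.0, Study Population:** "Clinical data will be collected at baseline and at regular post-enrollment follow-up until trial ends". Sections 2.0 and 13.0 set follow-up at 180 days, with visits at 30, 90 and 180 days.
- **Section 4.0:** "participants will be randomly assigned in a 1:1 ratio", with N=100.
- **Section 5.0:** changes to the Lavare cycle "will be made by the study staff according to the group you are assigned". No blinding of the investigator is described. The remark in Section 9.0 on treatment-revealing data concerns only when such data enter the database.
- **Section 6.0:** depleted left-heart volume "can increase the chances of suction events or low flow alarms" when the Lavare cycle is used. The section presents this as hypothetical.
- **Section 7.0:** an adverse event is defined broadly, as an untoward occurrence regardless of cause. For serious events, "Follow-up information on SAEs must also be reported by the Investigator within the same time frame". All deviations must be reported, with any mitigating circumstances or clinical reasoning.
- **Section 11.0:** "Multivariable regression analyses will be performed to assess for risk of primary and secondary outcomes with Lavare cycle on and off", with significance at p<0.05. It gives no analysis population, missing-data rule or censoring rule.

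**The concern.** The removal rule operates after randomisation, is discretionary, and rests with people who may know the arm. If those removed differ in prognosis from those kept, and the number removed or that difference in prognosis is not the same in both arms, the comparison of those who remain is no longer the randomised one.

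The triggering event should already be on record as an adverse event. What can be lost is what follows it: later components of the composite, death, KCCQ, 6-minute walk and biomarkers. Two things are at stake: the between-arm tests planned at p<0.05, and the event and retention rates that a feasibility pilot hands to a later trial. Outcomes that were never collected cannot all be recovered afterwards.

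**Working it through.** **Step 1. What triggers a drop.** *Untoward effect* is not defined. Two readings are open.

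- Broad: read with the adverse event definition in Section 7.0, it covers both arms alike and could include components of the primary composite (Section 2.0).
- Narrow: read as an effect of the intervention, the only candidates named are the hypothetical suction events and low-flow alarms of Section 6.0. These belong to the Lavare cycle, so triggers could differ by arm.

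**Step 2. Does any section require follow-up after a drop?** Sections 2.0 and 13.0 give a general schedule and are silent on dropped participants. The serious-event rule in Section 7.0 follows the event, not later outcomes. The deviation rule in Section 7.0 produces a documented reason for the plan-violation route, but does not keep the participant in follow-up. Section 11.0 does not say who is analysed. None closes the gap.

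**Step 3. Size, as illustration only.** The plan has no figure to reproduce: N=100 comes without an event rate, effect size or dropout allowance.

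From the documents: 100 participants at 1:1, so about 50 per arm; significance level 0.05 (two-sided assumed, as sidedness is not stated).

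Assumed: no true effect; 3 or 5 of 50 affected early; composite risk 30% or 50% in them and 10%, 15% or 20% in the rest; dropped participants vanish from both numerator and denominator.

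Let q be the share dropped and ρ the risk in the dropped divided by the risk in the kept. Then

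full rate = kept rate × (1 − q + qρ)

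apparent RR / true RR = (1 − q_Off + q_Off ρ_Off) / (1 − q_On + q_On ρ_On)

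This equals 1 if ρ = 1 in both arms, or if q and ρ are each the same in both arms. Equal numbers dropped are not enough.

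Example: 50%/10%, 5 of 50 dropped in On only. Full rate = 0.10×0.50 + 0.90×0.10 = 0.14; kept rate = 0.10; RR = 0.10/0.14 = 0.714. Dropped in Off only: 0.14/0.10 = 1.40.

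| Risk in affected / rest | On only, 3 of 50 | On only, 5 of 50 | Off only, 3 of 50 | Off only, 5 of 50 |
|---|---|---|---|---|
| 30% / 10% | 0.893 | 0.833 | 1.120 | 1.200 |
| 30% / 15% | 0.943 | 0.909 | 1.060 | 1.100 |
| 30% / 20% | 0.971 | 0.952 | 1.030 | 1.050 |
| 50% / 10% | 0.806 | 0.714 | 1.240 | 1.400 |
| 50% / 15% | 0.877 | 0.811 | 1.140 | 1.233 |
| 50% / 20% | 0.917 | 0.870 | 1.090 | 1.150 |

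Less extreme: at 50%/15% with only half of the affected dropped in one arm, and 5 affected, the kept rate is (0.05×0.50 + 0.90×0.15)/0.95 = 0.168 against a full rate of 0.185. The RR is 0.91 (On) or 1.10 (Off). With 3 affected it is 0.94 or 1.06.

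Equal numbers, unequal prognosis: 5 of 50 dropped in each arm, true rate 18.5% in both, On drops unrelated to risk, Off drops at 50% against 15%. RR = 0.185/0.150 = 1.23; reversed, 0.81.

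**Step 4. Compare with sampling error.** At 18% risk and 50 per arm, SE(log RR) = √(2×0.82/(50×0.18)) = 0.427. The 95% interval around 1.0 is exp(±1.96×0.427) = 0.43 to 2.31. Every shift above lies inside it.

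**Step 5. Effect on the test.** Exact enumeration, pooled two-sided z test, full arm at the average risk. At 50%/15%, deleting 5 of 50 in one arm gives a type I error of 0.074, against 0.053 with no drops; deleting 3 gives 0.060. At the most extreme pair (50%/10%, 5 of 50) it is 0.088, against 0.055.

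**The case against.** The strongest reply has four parts.

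*The illustration deletes people whose triggering event is on record.* This stands. Section 11.0 does not say that dropped participants are excluded. If their data up to the drop are kept, the shift would usually be smaller. If the trigger was itself a composite event and is counted, a yes/no composite loses nothing for that person. The 0.71 to 1.40 range is an upper-end scenario, not the expected effect of the clause.

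*The clause is the same for both arms, and the broad reading of its trigger is arm-neutral.* This also stands, so a difference by arm is only a possibility. A neutral clause does not guarantee neutral use where no blinding is described.

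*The schedule already covers everyone, and deviations are documented.* This stands in part. Universal follow-up may be the intention, and deviation reporting partly serves as a withdrawal log. But Section 10.0 removes the person from the trial, no text says that visits continue, and up to four sites could read it differently.

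*It is a feasibility pilot.* This is true and lowers the stakes, and no stated decision depends on the p-value. Section 11.0 nevertheless plans between-arm tests of the primary and secondary outcomes.

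Three stronger readings are tempting and not supported:

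- A reader might infer an as-treated analysis from the on/off wording in Section 11.0. It most naturally repeats the arm labels of Section 4.0.
- A reader might infer serious inflation of false positives. Removing a quarter or half of would-be event participants from one arm before their event is recorded, at 20% risk, gives a type I error of 0.084 or 0.218. Nothing in the documents suggests removal on that scale.
- A reader might infer that the later trial would be missized. With equal, equally prognostic deletions at 50%/15%, the pilot would show 15.0% instead of 17.1% to 18.5%. That misleads only if the later trial follows dropped participants; under the same rule, the lower rate would be the relevant input.

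**Conclusion.** The concern holds as a gap in the plan's wording. As written, the plan permits loss of later outcomes that is related to outcome and possibly to arm; it does not show that such loss will occur, or in which direction it would push the result. The conclusion rests on the removal rule in Section 10.0 together with the absence of any follow-up-after-drop rule or all-randomised statement, not on the risk-ratio range.

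The size is unknown. All event risks and drop counts used here are assumptions, and even the full-deletion results lie inside pilot sampling error. The change is worth making because it is cheap and because an ordinary confidence interval would not reflect this bias.

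**What to change.** **Section 10.0.** State that a change or stop of the assigned setting, an adverse event, a protocol deviation, or an investigator or sponsor withdrawal does not by itself end outcome follow-up. Collect clinical events and vital status to day 180, at visits where the participant is willing and otherwise by chart, unless consent to data collection is withdrawn. Record transplantation as an outcome, and state in advance whether it is a competing or a censoring event for pump-related outcomes. Report withdrawals by arm, date and reason.

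**Section 11.0.** State that the primary comparison includes all randomised participants in the arm assigned and keeps all data collected, including data up to and after a drop.

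**Cost.** Wording in two sections, a withdrawal record in REDCap, and a little extra visit or chart follow-up. No added participants and no visits beyond the existing schedule. Chart review will not recover KCCQ, and 6-minute walk and biomarkers may also be missing; report that missingness by arm. No position is taken on when a setting should be changed or stopped.

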### **11.0 Statistical analysis**

Statistical analysis will be performed using software STATA version 13 (StataCorp, College Station, TX). Baseline characteristics will be compared using Wilcoxon-Rank Sum test for continuous variables and Fisher's exact test for categorical variables. Multivariable regression analyses will be performed to assess for risk of primary and secondary outcomes with Lavare cycle on and off. Changes in laboratory parameters, echocardiographic measures, functional status and quality of life will be assessed using multivariable regression analyses. Statistical significance will be defined as  $p<0.05$ .

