#### **Visit 4: Day 180 (+/- 30 Days)**

- Review of Medical History
- Blood sampling for biomarkers (approximately 20 mLs)
- KCCQ questionnaire
- 6-minute walk test (Can be deferred if patient is on inotropic or MCS support)
- NYHA functional class assessment defined as follows:
  1. Class I - No symptoms and no limitation in ordinary physical activity, e.g. shortness of breath when walking, climbing stairs etc.
  2. Class II - Mild symptoms (mild shortness of breath and/or angina) and slight limitation during ordinary activity.
  3. Class III - Marked limitation in activity due to symptoms, even during less-than-ordinary activity, e.g. walking short distances (20-100 m). Comfortable only at rest.
  4. Class IV - Severe limitations. Experiences symptoms even while at rest. Mostly bedbound patients.
  5. No NYHA class listed or unable to determine.
- LVAD data: Standard parameters displayed on the screen upon routine interrogation of the LVAD will be collected. We will also ask Medtronic to provide trends in the LVAD parameters over past 30 days utilizing log-files that are stored in their data bank. **Please send log-files to Medtronic with a title: Lavare Trial Log-Files for appropriate storage and analysis.**
- Adverse events

Data will be collected on the following tests that were likely performed as part of the standard LVAD evaluation. The participant will not be required to undergo these tests for the purposes of this trial:

- Echocardiogram
- Right heart catheterization or Swan-Ganz Catheterization

Schedule of Events		At the time of randomization	30-day Visit (+/- 14 days)	90-day Visit (+/- 14 days)	180-day Visit (+/- 30 days)
Demographics	Age, gender, race	X			
Comorbidities	Etiology of heart failure, Atrial arrhythmia, Ventricular arrhythmia, Hypertension, Diabetes, Hyperlipidemia, Cerebrovascular event Peripheral arterial disease, Cancer, Chronic kidney disease and its stage, Dialysis, COPD, Obesity, Presence of pacemakers/ ICD (BiV/ dual/ single), Prior cardiac surgery, History of sternotomy, Number of sternotomies, History of hypercoagulable disease, History of prior DVT, History of prior PE, History of HIT	X			
Laboratory values	Basic chemistry panel, Complete blood count with differential, Liver function test, INR, LDH, Urine analysis	X	X	X	X
Biomarkers	NT-pro-BNP, ST-2, GDF-15, Galactin-3, Hs-CRP, TNF-alpha, IL-6, NGAL, KIM-1, TIMP-2, IGFBP-7, Ang-2, Ang-1, Soluble Tie-2, VEGF, Thrombin, vWF,	X	X	X	X

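### One unadjusted p<0.05 rule covers the primary and all secondary outcomes, including at least 17 biomarkers at three follow-up visits, so the chance of a false-positive biomarker result is far above 5%

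*Combined protocol and SAP*

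**What the plan says.** Section 11.0 is a single paragraph. On the treatment comparison it says: "Multivariable regression analyses will be performed to assess for risk of primary and secondary outcomes with Lavare cycle on and off". On change outcomes it says: "Changes in laboratory parameters, echocardiographic measures, functional status and quality of life will be assessed using multivariable regression analyses". It closes with the threshold, "Statistical significance will be defined as" p<0.05, and does not restrict that threshold to any outcome.

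In Section 2.0, item d of the secondary outcomes is "Changes in biomarkers", with no marker singled out. The biomarker row of the Schedule of Events in Section 5.0 lists "NT-pro-BNP, ST-2, GDF-15, Galactin-3, Hs-CRP, TNF-alpha, IL-6, NGAL, KIM-1, TIMP-2, IGFBP-7, Ang-2, Ang-1, Soluble Tie-2, VEGF, Thrombin, vWF". That is 17 markers, and the extracted list ends in a comma, so 17 is a minimum. The row is marked at randomization and at all three follow-up visits. Section 2.0 gives the timing: "follow-up visits will be logged at 30-days, 90-days and 180-days".

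The documents contain no multiplicity adjustment, testing order, main time point for the biomarkers or exploratory label for the secondary outcomes.

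**The concern.** A 5% threshold limits the false-positive risk of one test. Applied separately to each marker in a panel, it does not limit the risk for the panel. Here the panel is large and sampled repeatedly, and the plan does not say how many tests will be run or which one counts for each marker. The analyst could run 17 tests or 51, or choose the visit after seeing the data, and still be following Section 11.0.

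The trial is a feasibility pilot for a larger study, so its secondary results are most useful as estimates. Under the stated rule, a marker that crosses 0.05 by chance may be reported as a significant effect of the Lavare cycle, and a reader could not tell it from a real one. The other secondary outcomes (mortality, survival to transplantation, six LVAD complications, rehospitalization, echocardiography, NYHA class, walk test and KCCQ) fall under the same rule and add to the count.

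**Working it through.** The plan states no family-wise error rate and gives no power calculation, so there is no figure of its own to reproduce.

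**Inputs from the documents**
- Threshold: 0.05 per test (Section 11.0). Sidedness is not stated; two-sided is assumed for the simulations.
- Markers: 17 (Schedule of Events).
- Follow-up visits with biomarkers: 3 (days 30, 90 and 180).
- Arms: two ("participants will be randomly assigned in a 1:1 ratio"), so one on-versus-off contrast per marker per visit.

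**Input assumed**
- Correlation between test statistics, which the documents do not give. The cases below use 0 to 0.7 between markers and 0 to 0.9 between visits.

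All results suppose that the Lavare cycle affects no marker.

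**Step 1. Number of tests.** The text fits either of two readings:
- one contrast per marker: 17 tests;
- each marker at each visit: 17 × 3 = 51 tests.

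**Step 2. Expected false positives** (number of tests × 0.05, whatever the correlation)
- 17 × 0.05 = 0.85
- 51 × 0.05 = 2.55

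**Step 3. Chance of at least one false positive, independent tests** (1 − 0.95^k)
- k = 17: 1 − 0.95^17 = 0.582
- k = 51: 1 − 0.95^51 = 0.927

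The binomial chance of two or more is 20.8% for 17 tests and 73.1% for 51.

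**Step 4. The same chance with correlation.** This was simulated with 100,000 draws of 17 × 3 normal test statistics, with equal correlation between markers, equal correlation between visits, and a two-sided 0.05 cut-off.

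| Between markers | Between visits | 17 tests | 51 tests |
|---|---|---|---|
| 0.3 | 0.6 | 49% | 81% |
| 0.5 | 0.7 | 39% | 67% |
| 0.7 | 0.7 | 27% | 50% |
| 0.7 | 0.9 | 27% | 40% |

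The 17-test column uses one visit, so it depends only on the between-marker correlation. Weaker correlation gives values between these and the independent case: for example, 0.2 between markers and 0.5 between visits gives 54% for 17 tests and 87% for 51.

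**Step 5. Effect of the proposed rule.** When no marker is affected, every flag is false, so the false discovery rate equals the chance of at least one flag. Benjamini-Hochberg at 5% across 17 contrasts gave a chance of 5.0% with independent tests and about 3% to 5% in the correlated cases of Step 4, against 27% to 58% without adjustment.

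**The case against.** The strongest case on the other side has four parts.

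**The number of tests is not fixed.** The schedule sets sampling times, not hypothesis tests, and Section 11.0 nowhere says that each marker is tested at each visit. One model per marker fits the text equally well. The sentence on change outcomes does not name biomarkers; they come under the rule through the general reference to secondary outcomes. This stands. A reader might infer that false-positive biomarker findings are close to certain, or that the rule is bound to declare some markers affected. The documents support neither. The 93% needs 51 separate tests, full independence and no true effect on any marker. Independence is implausible for repeated samples from the same patients and for related markers such as Hs-CRP, TNF-alpha and IL-6.

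**No stated decision depends on a biomarker.** A reader might infer that a chance finding would set the next trial's endpoint. Nothing in the documents says so. Section 2.0 frames the future trial around pump-related complications, and the primary outcome here is a clinical composite. This also stands: the harm shown is misleading significance claims, not a wrong endpoint choice.

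**It is a pilot, and adjusting secondary outcomes in a pilot is partly convention.** This lowers the weight but does not remove the point. The plan does not leave secondary results descriptive; it attaches a significance rule to them, and no sample-size reasoning supports confirmatory use of any secondary test.

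**Dropping significance claims and setting a false discovery rate pull against each other.** This is fair if both are required together. The fix below makes reporting without significance claims the default and uses the false discovery rate only if markers are to be flagged.

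**Conclusion.** The point holds. Section 11.0 applies one unadjusted 0.05 rule to the primary and all secondary outcomes, with a panel of at least 17 markers at three follow-up visits and no main time point, exploratory label or error control. If no marker is affected, a false-positive biomarker result is more likely than not when tests are independent: about 58% with one test per marker, and up to about 93% with 51 visit-by-visit tests. Under the assumed correlations in the table, the risk is roughly 27–49% for 17 tests and 40–81% for 51. The lowest of these is still more than five times the nominal 5% (0.27 / 0.05 = 5.4).

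The exact figure depends on two things the documents leave open: the number of tests and the correlation between them. The conclusion that the risk is far above 5% holds in every case computed. The practical weight is moderate, because the biomarkers are secondary outcomes in a feasibility pilot and the primary composite is not undermined.

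**What to change.** Amend Section 11.0 as follows.

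1. Limit the p<0.05 rule to the primary composite.
2. State that all secondary outcomes are exploratory and reported as estimates with 95% confidence intervals, without significance claims.
3. For the biomarkers, specify one baseline-adjusted repeated-measures model per marker with one pre-named contrast. Day 180, the end of follow-up, is one candidate. It also has the widest visit window (±30 days) and is the visit most exposed to loss through death or transplantation, so the choice should be justified in the text.
4. If any marker is to be flagged as a signal, base the flag on Benjamini-Hochberg adjusted values (5% false discovery rate) across the 17 contrasts, not on unadjusted p<0.05. If none is to be flagged, item 2 is enough.

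The cost is a few sentences in the statistical section. Visits, sampling and sample size do not change. The downside is fewer nominally significant secondary results.
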